**Application for Review of Human Research: IRB Protocol Summary
Biomedical Research**

Section II

Principal Investigator: [name].

PROTOCOL TITLE

1. Full Title

Connected Health Blood Pressure Monitoring In Stroke and TIA Patients

2. Brief Title

Connected BP Study

STUDY SPONSORSHIP

1. Funding Sponsor

Penn Medicine Center for Healthcare innovation

2. Primary Sponsor

Study Summary

The goal of this pilot project is to assess adherence with home blood pressure monitoring in hypertensive patients with a history of stroke and to determine if a social incentive improves adherence with monitoring. Enrolled subjects stroke (Ischemic stroke, intraparenchymal hemorrhage, or high-risk TIA) and uncontrolled blood pressure, defined by SBP>140 or DBP>90 mm Hg at the time of study screening. To be eligible subjects will also be required to own a smart phone (iOS or Android operating system). After enrollment, patients will be given a home blood pressure cuff with instructions to monitor their BP twice daily for 90 days. Subjects will be randomly assigned to a social incentive program, in which a social supporter receives updates via email and/or text message on the subject's adherence with BP monitoring and their average blood pressure. This study will provide important pilot data which will inform the design of future studies utilizing connected health and automated systems to improve home blood pressure monitoring and blood pressure control in patients with a history of stroke.

1. STUDY OBJECTIVES

1.1 Primary Objective

The primary objective of this pilot study is to quantify adherence to 90 days of home blood pressure monitoring and to determine if a social incentive improves adherence.

1.2 Secondary Objective

A secondary objective of this study is to determine if adherence with blood pressure monitoring is associated with change in blood pressure during the study period and to determine which individual factors are associated with adherence.

2. OUTCOME VARIABLES

2.1 Primary Endpoint

Adherence with home blood pressure monitoring, defined by the proportion of home blood pressure recordings successfully completed.

2.2 Secondary Endpoints

Secondary endpoints include the following:

- Change in blood pressure over the 90 day study period
- Number of physician visits
- Number of emergency department visits
- Number of phone calls to the study team
- Number of changes in antihypertensive medications (dose adjustment or addition of a new agent)
- Patients perception of blood pressure monitoring device ease of use
- Patients perception of the utility of blood pressure monitoring
- Patients perception of blood pressure control

3. BACKGROUND

Stroke is the fourth leading cause of death and a leading cause of adult disability in the US, with over 800,000 cases per year.¹ Total direct and indirect costs from stroke are expected to increase from 72 Billion in 2012 to 183 Billion in 2030.² Effective secondary prevention strategies exist, including blood pressure control, high dose statin therapy, smoking cessation, diet, and exercise. The goal of this proposal is to perform important preliminary work on the feasibility of connected health and behavioral/social incentives to improve blood pressure control in patients with TIA or stroke.

Hypertension is by far the most significant risk factor for both ischemic stroke and intracerebral hemorrhage, with a population attributable risk of 35 to 75% depending on the definition of hypertension used.³ Approximately half of hypertensive patients with stroke continue to have suboptimally controlled blood pressure levels, and prior work suggests that stroke patients are even less likely to achieve target blood pressure goals than patients with coronary artery disease.⁴ Importantly, treatment to lower blood pressure reduces future stroke in those with and without a prior history of stroke.⁵⁻⁷ In a study of 227 ischemic stroke patients with symptomatic intracranial stenosis and a median follow-up of 32 months, 17% of subjects who achieved a systolic blood pressure of <140 (or <130 for diabetics) had a recurrent stroke, MI, or vascular death, compared to 29% in patients who did not achieve goal blood pressure.⁸ All of these 227 patients were all enrolled in a clinical trial and were receiving protocol driven intensive medical therapy to optimize risk factor control. Despite this, only 121 of 227 (53%) reached their goal blood pressure.

Non-adherence to prescribed medications has been proposed as one major reason for suboptimal blood pressure control.⁹ In one study of 4068 elderly subjects with hypertension, antihypertensive prescriptions were filled for only 49% of the prescribed medication days, and only 23% of subjects had good compliance (defined as taking > 80% of their recommended medication regimen).⁹ Additionally, lack of insight into the benefit of aggressive blood pressure control, lack of awareness of actual blood pressure levels, and lack of effective strategies for triggering more intensive therapy for both patients and providers may all be important.¹⁰

One prior study compared home blood pressure monitoring with intermittent nurse support to usual care in patients with recent stroke.¹¹ At 12 month follow-up, more patients in the intervention group had changes to their antihypertensive therapy (60% vs. 48%, p=0.02), but there was no overall difference in change in mean systolic blood pressure from baseline to 12 month measurements. This study was limited in that the incentive (nursing support) is relatively resource intensive, patient report was used to assess compliance rather than automated device recording, and blood pressure was checked infrequently (weekly).

The proposed study builds on existing literature in several unique and important ways. First, the blood pressure monitor used in this study is a commercially available unit that will interact with the subject's smart phone. Software that comes with the device will allow the subject to track their own blood pressure. Blood pressure will be checked more frequently (twice daily). Finally, the incentive used in this study will provide real time feedback to the subject and to a social supporter that they identify, in an effort to improve adherence.

4. CHARACTERISTICS OF THE STUDY POPULATION

4.1 Target Population

Adult subjects with a history of acute ischemic stroke, intraparenchymal hemorrhage, or high risk transient ischemic attack (TIA) and uncontrolled hypertension, defined by SBP>140 mm Hg or DBP > 90 mm Hg.

4.2 Accrual

The study will enroll a total of 90 patients at the Hospital of the University of Pennsylvania (HUP).

The study will be powered on the primary objective of the study, which is to compare adherence with twice daily blood pressure monitoring in subjects with and without a social incentive. Based on data in other study populations, we expect a 50% adherence rate in subjects without a social incentive.

A sample size of 90 subjects will provide 80% power to detect a 30% difference in adherence between groups. This calculation is based on a two-sample comparison of means, with $\alpha=0.05$.

Patients will be identified from the inpatient stroke service and the outpatient neurology clinic at the Hospital of the University of Pennsylvania. It is expected that we will complete enrollment in 15 months and the study will be completed in 2 years.

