8. STATISTICAL ANALYSIS

Demographics and past medical history variables will be summarized for all subjects using means or medians as appropriate for continuous variables and proportions for categorical variables. We will compare the two study arms using Student's t-test or Wilcoxon rank sum as appropriate for continuous variables and χ^2 test for categorical variables.

The primary outcome measure is adherence with blood pressure monitoring during the study period. Adherence will be defined by dividing the number of successfully completed BP measurements (numerator) by the expected number of BP measurements (denominator). The expected number of BP measurements is the number of days that the subject is in the study multiplied by 2. Most subjects will be enrolled in the study for 90 days and will therefore be expected to check their BP 180 times. Adherence in this case is the number of completed BP measurements divided by 180. The 90-day follow-up visit has a window of +/- 7 days, so for subjects that complete the study protocol the denominator will be adjusted accordingly. Subjects whom withdrawal from the study and/or stop monitoring their BP before the 90-day follow-up visit will remain in the analysis. These subjects will be considered non-adherent for all BP measurements after they cease taking measurements and the denominator will be set at 180. As an example, if a subject checks their BP 60 times in the first 75 days of the study and then ceases all BP measurements, adherence will be calculated as $60/180=33.3\%$. After adherence has been calculated for all subjects we will evaluate the distribution of adherence for normality and compare adherence between the two study arms using Student's t-test or Wilcoxon rank sum as appropriate. A sample size of 90 will give us 80% power to detect a 30% difference between groups with $\alpha=0.05$.

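### Does N=90 really give 80% power for a 30% difference in adherence when no standard deviation is stated?

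*Combined protocol and SAP*

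**What the plan says.** The primary endpoint is adherence to home blood pressure checks, "defined by the proportion of home blood pressure recordings successfully completed" (Section 2.1). Section 8 computes it for each subject as completed over expected readings, with 180 expected over 90 days. The plan is then to "compare adherence between the two study arms using Student's t-test or Wilcoxon rank sum as appropriate".

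Section 4.2 gives the planning value for controls: "Based on data in other study populations, we expect a 50% adherence rate in subjects without a social incentive". It then says "A sample size of 90 subjects will provide 80% power to detect a 30% difference in adherence between groups" and adds "This calculation is based on a two-sample comparison of means", with alpha 0.05. Section 8 repeats the claim: "A sample size of 90 will give us 80% power to detect a 30% difference between groups". Neither section gives an SD, the sidedness, the scale of the 30%, or the source of the 50%.

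Section 3 describes an outside study of 4068 elderly hypertensive subjects in which "antihypertensive prescriptions were filled for only 49% of the prescribed medication days, and only 23% of subjects had good compliance", good compliance being "defined as taking > 80% of their recommended medication regimen". It is cited there to explain poor blood pressure control and is not linked to the sample size.

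**The concern.** A comparison of means cannot be sized without an SD, so the one sentence that justifies the size of the primary comparison cannot be checked as written. The Section 3 study reports 49%, close to the 50% planned for controls, and also gives a tail fraction. It is tempting to turn those two figures into an SD. Doing so with a beta distribution gives about 0.316. The 80%-power difference then comes out near 19 percentage points instead of 30, with about 99% power if 30% is absolute and about 61% if it is relative.

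If that were established, the plan would misstate what the trial can detect. On the relative reading it would also miss its intended effect about four times in ten. A later trial sized on the SD implied here could be wrong as well, which matters in a pilot meant to inform later work.

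**Working it through.** **Inputs.** 90 subjects allocated 1:1, so n = 45 per arm (Sections 4.2 and 7.1). Alpha 0.05, 80% power and 50% in controls (Section 4.2). Two-sided testing is assumed. Each subject's adherence is taken to lie between 0 and 1.

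**Formulas.** Normal approximation: n per arm = 2(1.960 + 0.842)² SD²/d². Power figures use the noncentral t with 88 degrees of freedom and noncentrality d/(SD·√(2/45)). Solving for 80% power gives d = 0.597 × SD.

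**1. Reproducing N=90.**
- Absolute, d = 0.30: implied SD = 0.30/0.597 = 0.50. Check: 2 × 7.85 × 0.25/0.09 = 43.6, so 44 per arm; by noncentral t, 45 per arm gives 80.4%.
- Relative, d = 0.15: implied SD = 0.15/0.597 = 0.25, with the same 44 to 45 per arm.
- Two proportions, 50% vs 80%: 39 per arm, or 45 with continuity correction.

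The stated N can therefore be reached by more than one route. The documents do not show which was used, and none of this shows a miscalculation.

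**2. What Section 3 can say about the SD.** Read 49% as the mean of per-subject adherence and 23% as the share above 0.80.

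| Assumed shape | SD | 80%-power difference (points) | Power, 30 points | Power, 15 points |
|---|---|---|---|---|
| Smallest possible on 0-1 | 0.169 | 10.1 | >99% | 99% |
| Beta | 0.316 | 18.9 | 99.4% | 60.5% |
| Normal clipped to 0-1 | 0.335 | 20.0 | 98.8% | 55.6% |
| Unbounded normal, 0.31/0.739 | 0.42 | 25.1 | 91.8% | 38.8% |
| Largest possible on 0-1 | 0.445 | 26.6 | 88.6% | 35.3% |

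- Beta: a+b = 1.508, so SD = √(0.49 × 0.51/2.508) = 0.316.
- Smallest: 23% at 0.80 and the other 77% at (0.49 − 0.23 × 0.80)/0.77 = 0.397.
- Largest: 23% at 1, (0.49 − 0.23)/0.80 = 32.5% at 0.80 and the rest at 0, so SD = √(0.23 + 0.325 × 0.64 − 0.49²) = 0.445.

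The figures of 19 points and 61% come from the shape chosen, not from the two reported numbers.

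**3. Absolute reading without Section 3.** On a 0-1 scale the SD at mean m cannot exceed √(m(1−m)), which is 0.50 at 0.50 and 0.40 at 0.80. The root mean square is √((0.25 + 0.16)/2) = 0.453. Noncentrality is at least 0.30/(0.453 × √(2/45)) = 3.14, so power is at least about 87%. Even if every subject were all-or-nothing, the 80%-power difference from 50% would be at most about 27.5 points.

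**4. Relative reading.** Power for 15 points is about 80%, 65%, 52% and 42% at SDs of 0.25, 0.30, 0.35 and 0.40.

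**The case for a change.** The strongest case for acting does not need Section 3. On the absolute reading, 30 points is not the 80%-power difference for this endpoint, because the SD of about 0.50 that it requires is out of reach when one mean is 0.80. The likely routes to 45 per arm, an SD of 0.50 or a continuity-corrected comparison of two proportions, both treat each subject as adherent or not, whereas Section 8 analyses a proportion per subject. On the relative reading, 80% requires an SD of 0.25 that appears nowhere. The unbounded normal is also a poor model for a proportion. Stating the inputs would cost only wording.

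Most of that is correct. The SD, the sidedness and the scale are missing, and the absolute statement is looser than it need be. But the error on that reading is in the safe direction: the trial has more power than promised. On the relative reading the gap is an unknown, not a demonstrated failure, since 0.25 lies inside the 0.17 to 0.445 range. The Section 3 figures concern prescription fills in another population. This trial studies twice-daily cuff readings, with automatic reminders to every subject, in smartphone owners without moderate or severe disability.

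The worry about later trials is also weak. They can use the SD observed here, and the SD implied by the sentence is 0.50 only if 30% is absolute. If it is relative, the implied SD is 0.25, and the sizing error at 0.316 would run the other way: (0.316/0.25)² = 1.6 times too small, not (0.50/0.316)² = 2.5 times too large.

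**Conclusion.** The concern does not call for a change. What stands is incomplete reporting: Sections 4.2 and 8 leave out the SD, the sidedness and whether 30% is absolute or relative. What does not stand is the claim that N=90 detects 19 to 20 points and not 30, or that power is about 60%; both rest on an SD that the documents neither state nor determine.

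With 45 per arm and two-sided alpha 0.05 assumed, the absolute reading gives at least about 87% power for 30 points, so the promised 80% is met with room to spare. The relative reading gives about 80% at SD 0.25 and about 42% at SD 0.40, and the documents cannot say where the truth lies.

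Supplying the missing inputs would leave the sample size, test, endpoint and conclusions unchanged. Writing a derived SD of 0.316 into the protocol would credit a cited study with a figure that the documents do not report for it, and would replace the sponsor's stated target with a debatable one. For a pilot of this size that is no gain.

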4.3 Inclusion Criteria

1. Adult, age ≥ 18 years
2. History of ischemic stroke, intraparenchymal hemorrhage, or high risk TIA (defined by ABCD2 ≥ 4) with the past 5 years prior to enrollment
3. Hypertensive at time of screening, defined by SBP >140 mm Hg or DBP >90 mm Hg
4. Enrollment must occur within 30 days of study screening
5. Must own a smart phone capable of interacting with the connected blood pressure cuff (Apple iPhone 3GS or higher; Android 4.0 or higher with Bluetooth connectivity)
6. Must be able to identify at least one adult (≥ 18) with internet access and/or a smart phone with text messaging capability who could serve as a social support person.
7. Willingness and ability to sign informed consent by patient

4.4 Exclusion Criteria

1. Moderate or severe disability, defined by modified Rankin Scale ≥ 3 .
2. Moderate or severe cognitive impairment, defined by a Mini-Mental Status Examination Score of ≤ 20
3. Expected residence in a rehabilitation hospital, nursing facility or assisted living community during the study period.
4. Upper arm circumference <9 inches or >17 inches
5. Inability to monitor BP in upper arms (i.e. history of bilateral radical mastectomy, bilateral severe subclavian stenosis, or bilateral arterial venous fistulas for dialysis).
6. Inability to follow-up at 90 days and return BP monitor
7. Active participation in another clinical trial
8. Pregnant women

4.5 Vulnerable Populations

Children, fetuses, neonates, prisoners and pregnant women are not included in this research study.

4.6 Subject Recruitment

4.6.1 Participant Screening and Recruitment

Potential study participants will be identified from the inpatient stroke service at the Hospital of the University of Pennsylvania and the outpatient neurology clinic at the Hospital of the University of Pennsylvania. Additionally, the neurology residents and the stroke physicians at the Hospital of the University of Pennsylvania will be

informed of the study and provided with contact info for study personnel to refer eligible outpatients. The attending physician caring for the patient will be informed of eligible patients prior to enrollment. Screening visits may include an inpatient admission for stroke or TIA or any routine outpatient clinic visits in which blood pressure is measured. Inpatients who are considered for the study can only be enrolled if they are being discharged to home, and enrollment should occur on the date of discharge. Patients discharged to an inpatient rehabilitation hospital or skilled nursing facility are excluded from participation.

4.6.2 Informed Consent

Informed consent must be obtained (completed online by the participant) prior to initiation of any study-related activity. Consent will be obtained via the Way to Health online platform. Way to Health is secure and HIPAA compliant.

4.6.3 Consent Process

After an eligible subject is identified, a member of the study team will contact the attending physician responsible for the patient's care to ensure that the patient is clinically suitable for the study. If so, the patient will be approached by a member of the research team for consent. The full consent form is enclosed as attachment 1. The consent form will be described to the patient in plain language. The patient will also be given a copy of the consent form for their reference. Electronic informed consent will be obtained via the Way to Health platform prior to the onset of any study related activities. The patient will have the ability to withdraw consent and exit the study at any time.

The physicians caring for the patient clinically will make judgments about capacity. All patients seen by neurology receive detailed neurologic examinations, which can be used to assess capacity. These examinations include an assessment of cognition, language function, and neglect/anosagnosia in addition to other domains of neurologic function. Additionally, the person obtaining consent will evaluate the subjects understanding of the risks/benefits of study participation by asking open-ended questions about the study and addressing any misperceptions or unanswered questions. Possible questions include: Can you describe the study in your own words? What more would you like to know? Would you please explain to me what we are asking you to do? What are your concerns? If a potential subject is not competent to consent for him or herself, they will be excluded from the study.

4.6.4 Waiver of Authorization

[figure not shown]
Not applicable

4.6.5 HIPAA Authorization

Following mandated federal HIPAA regulations and according to local IRB guidelines, the use and disclosure of the subject's protected health information (PHI) will be explained and participant authorization will be obtained as part of the informed consent process. The consent forms will list those individuals and organizations that may have access to the participant's research data. HIPAA authorization will be included in the informed consent process. The HIPAA authorization form is attached as a part of the informed consent form in attachment 1.

4.6.6 Patient Flow

A depiction of patient flow is presented below:

4.6.7 Follow-up Period

Participants will have a follow-up phone call at 48-72 hours after enrollment and either a phone or computer based encounter 30 days +/- 3 days after enrollment and an in-person visit at 90 days +/-7 days. Participation will be completed after the day 90 visit.

5. STUDY DESIGN

5.1 Phase

Phase 2 pilot trial.

5.2 Design

This is a single center randomized trial designed to assess the effectiveness of a social intervention to improve adherence with home blood pressure monitoring. Computer-based block randomization (block size=4) will be used to maintain relatively equal numbers of subjects in both arms of the study. This study will provide important preliminary data for future studies, which will use behavioral incentives to improve adherence to home blood pressure monitoring and titration of antihypertensive therapy.

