5.3 Study Duration

Individual subjects will be in the study for a total of 90 days. They will receive a telephone call at 48 hours and either a computer based or telephone based interview at 30+/- 3 days and then will have an in-person visit at 90+/-7 days.

Total study duration is expected to last approximately 2 years. We expect to enroll about 6 subjects per month and should reach our target of 90 patients by 15 months. The final follow-up visit will occur 3 months after the last patient is enrolled. Data collection and analysis will be completed in the subsequent 6 months for total study duration of 24 months.

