Patients will be randomly assigned (1:1) to either receive a social incentive or not. The social incentive will require the subject to identify a social supporter. This individual can be a family member, friend, or other community member selected by the subject. The social supporter will need to assent to the study and register on the Way to Health platform. The social supporter will receive education on the importance of hypertension, how to measure blood pressure, and how to operate the Withings monitor. If the social supporter is not present at the time of subject enrollment, they may assent to the study via telephone and/or by registering online at the Way to Health platform. In this scenario they will receive education via telephone and/or online.

The social supporter will choose whether they prefer to receive study communications via text message or email. The social supporter will receive a text or email message alert at 11:00am if the subject has not completed their morning BP reading and at 9:00pm if the subject has not completed their evening BP reading. The social supporter will also receive feedback on the subject's BP control from the Way to Health platform on a weekly basis. This message will summarize the subject's adherence to home monitoring in the preceding 7 days. It will also contain the subject's mean BP over the preceding 7 days and note whether the subject's BP is above or below a goal of <140/90 mm Hg. The expectation is that the social support person will provide further feedback to the subject in order to improve both adherence and BP control.

Non-adherence

BP readings will be automatically uploaded from the subject's smartphone to the Way to Health platform. If the subject goes 7 days without a single BP measurement, Way to Health will alert study personnel. Study personnel will contact the subject by phone to remind them to check their BP and troubleshoot any potential technical

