14. RESOURCES NECESSARY FOR HUMAN RESEARCH PROTECTION

This research protocol will be conducted by the clinical research section of the stroke division of the department of neurology. The research team consists of three full time clinical research coordinators, one nurse practitioner, three vascular neurology fellows, and five vascular neurology attendings. All members of the research team will be required to have Patient Oriented Research training through the University of Pennsylvania Knowledge Link training system. All members of the research team who will be assessing NIHSS and mRS will be trained in the administration of these scales using web-based training systems. The research team will maintain training records, including copies of all pertinent certificates.

Prior to initiation of the study, the research team will have an in-service session to review the study protocol and procedures in detail. While the study is underway, the research team will meet weekly to discuss the study, including enrollment, follow-up, and any other issues which may arise.

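### A fixed block size of 4, disclosed in a single-centre protocol, could let recruiting staff who track past assignments foresee about a third of them on average; undisclosed, randomly varying sizes would remove most of that certainty at almost no cost.

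*Combined protocol and SAP*

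**What the plan says.** Section 5.2 describes the trial: "This is a single center randomized trial designed to assess the effectiveness of a social intervention". It then gives the allocation method: "Computer-based block randomization (block size=4) will be used to maintain relatively equal numbers of subjects in both arms of the study". Section 7.1 (Social Incentive) gives the ratio: "Patients will be randomly assigned (1:1) to either receive a social incentive or not". Section 4.2 sets the size: "The study will enroll a total of 90 patients". Section 5.3 gives the pace: "We expect to enroll about 6 subjects per month".

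No stratification factor is named, so there is a single allocation sequence. The documents contain no rule on concealing the next assignment and no statement on blinding.

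Three further passages bear on what staff could know:

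- Section 14, on preparation: "Prior to initiation of the study, the research team will have an in-service session to review the study protocol and procedures in detail". The block size is in the text they review.
- Section 14, on the conduct of the study: "the research team will meet weekly to discuss the study, including enrollment, follow-up, and any other issues which may arise".
- Section 7.1, on the incentive arm: "The social supporter will receive education on the importance of hypertension, how to measure blood pressure, and how to operate the Withings monitor". The supporter also has to assent and register on the platform.

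Section 8 compares adherence between arms by t-test or Wilcoxon rank sum test, with no covariate adjustment.

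**The concern.** With two assignments to each arm in every block of four, the end of a block follows from its beginning. Generating the list by computer hides the list, but it does not prevent this deduction by someone who knows the block size and the earlier assignments.

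The primary endpoint is a behaviour that staff can partly anticipate from a patient's motivation or ease with a smartphone. A recruiter who foresees the next arm could, knowingly or not, be more or less inclined to approach a particular patient. For outpatients the recruiter could also time the approach, since section 4.3 allows up to 30 days between screening and enrollment. At 6 subjects a month that window covers about 6/4 = 1.5 blocks.

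Selection of this kind acts before randomisation. It would shift the adherence comparison directly, and the unadjusted primary test would not remove it.

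**Working it through.** The plan gives no figure for predictability, so there is none to reproduce.

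**Inputs from the documents.** Block size 4 and one centre (section 5.2); 1:1 allocation (section 7.1); N = 90 (section 4.2), taken as 45 per arm; alpha 0.05 (section 4.2), taken as two-sided.

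**Assumed inputs.** A shift of d = 5 or 10 adherence points in the subjects placed on foreseen slots, and an SD of adherence of 30 to 40 points. The documents give neither.

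**1. Certain assignments in one block.** A 2+2 block has 6 equally likely orders, hence 6 × 4 = 24 positions. Positions 1 and 2 are never certain. Position 3 is certain when the first two assignments match, which happens in 2 of 6 orders. Position 4 is always certain.

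- Expected number certain per block = 1/3 + 1 = 1.333
- Share = 1.333/4 = 33.3% (8 of 24 positions)

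**2. Over 90 subjects.** 90 = 22 full blocks + 2 subjects, and the last two are never certain.

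- Expected number certain = 22 × 1.333 = 29.3
- Share = 29.3/90 = 32.6%
- Possible range = 22 to 44 subjects (24.4% to 48.9%)

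**3. Best guess.** Guess the arm with more places left in the block, and count a tie as one half. Expected correct by position:

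- Position 1: 1/2
- Position 2: 2/3
- Position 3: (1/3)(1) + (2/3)(1/2) = 2/3
- Position 4: 1

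The sum is 2.833, so success is 2.833/4 = 70.8% per block. Over 90 subjects it is (22 × 2.833 + 1/2 + 2/3)/90 = 70.6%. Chance gives 50%.

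**4. Illustrative bias from certain slots.** Suppose every certain slot in one arm receives a subject d points above average, and every certain slot in the other arm a subject d points below. With share f certain, bias in the arm difference = 2 × d × f.

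- d = 5: 2 × 5 × 1/3 = 3.3 points
- d = 10: 2 × 10 × 1/3 = 6.7 points (6.5 with f = 32.6%)

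**5. Effect on type I error.** Non-centrality = bias / (SD × √(2/45)), where √(2/45) = 0.211; two-sided t-test with 88 df.

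| d | SD | Bias | Non-centrality | Type I error |
|---|---|---|---|---|
| 5 | 40 | 3.3 | 0.40 | 6.8% |
| 5 | 30 | 3.3 | 0.53 | 8.2% |
| 10 | 40 | 6.7 | 0.79 | 12.2% |
| 10 | 30 | 6.7 | 1.05 | 18.1% |

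**6. What randomly varying sizes would change.** These rows come from simulated sequences of 90 (1,000 per setting). Staff are assumed to know the set of sizes and all past assignments, but not where each block ends.

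| Block sizes | Known with certainty | Best guess correct |
|---|---|---|
| Fixed 4 (exact) | 32.6% | 70.6% |
| Random 4, 6 | 5.7% | 69.1% |
| Random 4, 6, 8 | 2.4% | 67.9% |

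**7. The same comparison for guess-based steering.** If staff act on the best guess at every slot, with success p, bias = 2 × d × (2p − 1).

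- Fixed 4, p = 0.708: 0.83d
- Random 4, 6 and 8, p = 0.679: 0.72d

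That is a reduction of about 14%. For certain-slot steering the bias falls from 0.67d to 2 × 0.024 × d = 0.05d.

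**The case against.** The strongest reply is that a reader might infer that staff will know one third of assignments, or that the adherence comparison is biased. The documents support neither statement.

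- **Tracking is not documented.** Certainty needs every earlier assignment, in order, and the block boundaries. Section 14 lists twelve team members (3 + 1 + 3 + 5), and section 4.6.1 has them recruiting from both an inpatient service and a clinic. Nothing says one person sees all assignments or that the same individuals recruit and follow every subject. This stands. One site, slow accrual and shared meetings make tracking plausible, no more.
- **Knowledge of arm is inferred.** The supporter may register online and be educated by telephone or online (section 7.1), and the platform applies the incentive automatically (section 6). This also stands, although ignorance of arm across the team is unlikely.
- **Discretion is limited.** Inpatients should be enrolled on the day of discharge (section 4.6.1), so timing is mainly an outpatient matter. Every subject must be able to name a supporter (section 4.3), which narrows selection on support. Most other criteria are objective. Choice of whom to approach remains, as does the judgement of clinical suitability before consent (section 4.6.3).
- **Adherence is recorded automatically** (sections 7.3 and 7.4). That protects measurement. It does not govern who is enrolled next.
- **This is a pilot.** It is, but sections 4.2 and 8 still present a powered comparison between arms.
- **The remedy does little against guessing.** This is correct on the figures above, and the gain should be described accordingly.

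**Conclusion.** The point holds as a conditional one. If recruiting staff track past assignments and see the arm, a disclosed fixed block of 4 would let them know about a third of assignments on average (32.6% of 90) and guess about 71% correctly.

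The bias of 3.3 to 6.7 points, and the type I error of about 7-8% (shift of 5 points) or 12-18% (shift of 10 points), are an illustration. They assume steering on every certain slot, always in the favourable direction and throughout the trial, with an assumed shift and SD. They are not an estimate of what will happen. Steering on best guesses as well would give a somewhat larger figure (0.83d against 0.67d) on equally unverified assumptions.

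The documents establish opportunity only. The change is worth making because it is nearly free, so this is best classed as a cheap improvement rather than a flaw that invalidates the design.

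**What to change.** In section 5.2, replace the stated block size with permuted blocks of randomly varying size (for example 4, 6 and 8). Hold the sizes in a randomisation file or restricted document that recruiting staff do not see. Add that the platform releases each assignment only after consent, eligibility and baseline data are locked. Consent before any study activity is already required (section 4.6.2), so the new elements are the eligibility and baseline locks.

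The cost is one platform setting and a sentence or two of text. The largest possible final imbalance rises from 2 subjects to 4 with a maximum block of 8. The gain is a fall in certain assignments from about 33% to about 2%. Best-guess success falls only from about 71% to 68%, so the change should not be presented as removing all scope for selection.
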